5.0 DATA COLLECTION AND MANAGEMENT

5.1 DATA PROCUREMENT

- For Aims 1, 2 and 3A, Drs. [name], [name] and [name] will seek to obtain the data in Tables 1 and 2 (below) from the EMR with the assistance of the Research and Informatics Scientific Computing Core (RISCC)
- For Aim 3B, data will be collected by the clinical pharmacist directly from each patient's medical chart
- For Aim 4A, interview data will be digitally recorded during each session. Interviews will be conducted by a PhD researcher from RAND, specifically trained in qualitative research.
- For Aim 4B, medication adherence data will be collected electronically through the MEMS-cap device. Additional data will be collected via survey instruments administered by study staff during clinic visits.
 - Video Diary Sub-Study for Aim 4B: During the first 3 weeks, we will prompt participants once a week to submit video diaries, although they will be encouraged to submit whenever they want to share or document something. The video diary prompts will be combined with (preceded by) 1-2 survey questions asking participants to quantify their level of satisfaction with the intervention overall or specific intervention components. Prompts and video diaries will be sent and documented using Medallia LivingLens, a secure platform designed to document remote video recordings for qualitative research. Participants will download the Medallia LivingLens application to their smart phone, which will be used to record their video diaries. Storage and security details of video diaries are located in section 5.5.
 - For all aims, data will be collected via EHR or REDCap based questionnaires. All captured data will be housed in a HIPAA-compliant secure storage system, such as REDCap or Box, within the Cedars-Sinai network with access restricted to only approved members of the research team.

5.2 TIME PERIOD OF DATA UNDER REVIEW

- Data will be reviewed from between the dates 1/1/2012 through 3/30/2019. For patients enrolled in the pilot study described in Aim 3B, data will be collected during the 9 week period of their participation.

- Data for Aims 1, 2 and 3A will be collected retrospectively. For Aim 3B, data will be collected weekly starting on the date of their in-person appointment and will be collected prospectively during the 9 week period of monitoring for each patient, estimated between the months of June and November, 2019. For Aim 4A, data will be collected during the interview discussions. For Aim 4B, data will be once per month during clinic visits for the first 3 months, and then every 3 months until 9 months after enrollment.
- Information will be kept for a total of 2 years following the initiation of the study.

5.3 VARIABLES COLLECTED

- For Aims 1, 2 and 3A, please refer to Tables 1, 2, and 3 for variables that will be collected.
- For Aim 4B, please refer to Table 4 for variables that will be collected.

5.4 SOURCE DOCUMENTS

- For Aims 1, 2 and 3A, we seek to obtain the data in Tables 1 and 2 from the EMR with the assistance of the Research and Informatics Scientific Computing Core (RISCC)
 - Table 1 contains patient level data to be obtained at the visit level
 - Table 2 contains medications to be obtained at the patient level for each visit. Data is to include if the medication has been prescribed and if so, at what dose and frequency. The prescribing provider and providers specialty will also be acquired.
 - Zip Code will be used to estimate population level sociodemographic factors from census data
- For Aim 3B, patient medical records will be the source document for the information identified in Tables 1 and 2, as well as information outlined in Table 3
- For Aim 4B, survey instruments will be the source document for the variables outlined in Table 4. Video diaries will be obtained and stored, as detailed in section 5.5.

Table 1 (Data collected for all aims)

Blood Pressure readings at each outpatient clinic visit
Provider Name at each visit
Provider Specialty at each visit
Provider demographic
ICD-9/ICD-10 codes
Dates of each clinic visit
Patient insurance information
Patient date of birth
Patient ZIP Code
Patient age
Patient gender
Patient ethnicity
Patient BMI at each visit
Primary Care Physician Name and Practice Location
Patient glomerular filtration rate at each clinic visit
Highest A1C level during study period

Table 2 (Data collected for all aims)

ACE-Inhibitors/Angiotensin Receptor Blockers	Beta-Blockers	Diuretics	Calcium Channel Blockers	Nitrates	Other
Lisinopril	Metoprolol	Hydrochlorothiazide	Amlodipine	Imdur	Hydralazine
Benazepril	Bisporolol	Chlorthalidone	Diltiazem	Isordil	Clonidine

Captopril	Carvedilol	Metolazone	Verapamil		Aliskiren
Enalapril	Propranolol	Lasix	Felodipine		
Fosinopril	Nadolol		Isradipine		
Ramipril	Atenolol		Nifedipine		
Perinodopril	Labetalol				
Losartan	Nebivolol				
Valsartan					
Candesartan					
Irbesartan					
Telmisartan					
Azilsartan					
Eprosartan					
Olmesartan					

Table 3 (Data collected for Aim 3B only)

Initial Visit (Week 0)	Baseline blood pressure
	Current medications (names, doses and frequencies)
	Laboratory values (basic metabolic panel, TSH and A1C)
Weekly Phone Call (Weeks 1-8)	Record all uploaded blood pressures in the EMR
	New/updated laboratory values
	Current medications (names, doses and frequencies)
	Changes to medications (names, doses and frequencies)
	Patient reason for missing or absent blood pressure data, if applicable

*Note, baseline demographic factors for patients enrolled in Aim 3B will already have been collected as part of Aim 1.

Table 4 (Data collected for Aim 4B only)

Survey measures (initial visit, month 3 visit, month 9 visit)	Behavior economic measurements (biases, behavioral automaticity, intrinsic motivation measures)
	Demographic and socioeconomic data (age, gender, education, employment, insurance type, income, marital status and housing)
	Medical factors (baseline blood pressure, number of non-antihypertensive medications on at baseline, final number of antihypertensive medications at the end of the study and history of cardiovascular disease)
	Physical symptoms/side effects of medications
	Structural barriers to medication adherence (insurance status, patient distance to pharmacy)
MEMS-cap electronic data (automatically captured)	Date of bottle opening (for hypertensive medication)
	Time of bottle opening (for hypertensive medication)

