We will create three time-to-care measures: time-to-diagnosis, for patients who qualify for new diagnoses; time-to-initiate, for the same patients; and time-to-intensify, for patients with established diagnoses. We will create two time-to-control measures, one for patients with new and one for patients with established diagnoses. The new time-to-care and time-to-control measures will be based on the 2017 ACC/AHA guidelines. We will define undiagnosed hypertension as two ambulatory blood pressures \geq 130/80 without an ICD-9/10 code for hypertension in the preceding year; uncontrolled hypertension will be defined using the same blood pressure criterion but patients will have an ICD-9/10 code for hypertension. A new diagnosis of hypertension will be defined as an ICD-9/10 code for hypertension without a prior code or antihypertensive medication use in the preceding year. We will define treatment initiation as the first prescription for an antihypertensive medication following a new diagnosis of hypertension. Treatment intensification will represent the addition of another antihypertensive medication, an increase in the dose of an existing antihypertensive medication, and a change from one antihypertensive medication to another. We will access the 2017 guidelines and other standard sources to develop a list of antihypertensive medications. Time to care will be calculated as the number of days from the last blood pressure above goal to the documentation of the diagnosis or the initiation/intensification of treatment. Time to control will be calculated as the number of days from the last blood pressure above goal to the first blood pressure at goal.

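### Table 2, the only stated list of drugs to pull from the EMR, does not match the antihypertensive definitions behind the Aims 2 and 3A measures

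*Protocol*

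**What the plan says.** **What is to be extracted.** Protocol Section 5.4 states: "For Aims 1, 2 and 3A, we seek to obtain the data in Tables 1 and 2 from the EMR". It adds "Table 2 contains medications to be obtained at the patient level for each visit", and for each drug: "Data is to include if the medication has been prescribed and if so, at what dose and frequency". Section 5.3 also sends the reader to the tables: "For Aims 1, 2 and 3A, please refer to Tables 1, 2, and 3 for variables that will be collected". Table 2 is a grid of named drugs. Three of its column headings read "Calcium Channel Blockers Nitrates Other", and the last of these columns is itself a closed list of three drugs.

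**What the measures need.** Protocol Section 4.0 builds three definitions on antihypertensive use:

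- A new diagnosis is an "ICD-9/10 code for hypertension without a prior code or antihypertensive medication use in the preceding year".
- Initiation is the first antihypertensive prescription after such a diagnosis.
- "Treatment intensification will represent the addition of another antihypertensive medication", or a dose increase, or a switch between drugs.

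For the drug list behind these definitions, Section 4.0 says: "We will access the 2017 guidelines and other standard sources to develop a list of antihypertensive medications". It does not mention Table 2, and Section 5.4 does not mention this planned list.

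**The concern.** The protocol has one list for extraction and promises another for analysis, and it does not connect them. An analysis list can be applied only to drugs that are in the extract. If the extraction list is the narrower one, a real treatment decision made with an unlisted drug leaves no trace in the data.

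This matters because the new measures are the main product of Aims 2 and 3A. Section 2.0 says that they should separate failure to recognise hypertension from failure to act and from insufficient action. Recording a real drug addition as no action blurs that distinction. Section 7.1 then relates the measures to control rates by physician and clinic and compares them between groups of clinics, so unequal use of unlisted drugs would enter those comparisons.

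**Working it through.** No sample-size or power figure is involved. The check is a count of Table 2, a comparison with Section 4.0, and an illustration of size.

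**1. Count of Table 2.** ACE inhibitors and angiotensin receptor blockers 15, beta-blockers 8, diuretics 4, calcium channel blockers 6, nitrates 2, other 3. Total: 15 + 8 + 4 + 6 + 2 + 3 = 38 names, or 38 − 2 = 36 without the nitrates. There is no catch-all entry and no wording that marks the names as examples.

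**2. What is absent.** That the drugs below are antihypertensives is general pharmacology, not a statement in the documents.

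- Classes with no entry: mineralocorticoid antagonists (spironolactone, eplerenone), potassium-sparing diuretics (amiloride, triamterene), alpha-1 blockers (doxazosin, terazosin, prazosin).
- Gaps in classes that are represented: quinapril, trandolapril and moexipril; torsemide and bumetanide; indapamide; minoxidil; methyldopa and guanfacine.
- Fixed-dose combination products are not addressed.
- Imdur and Isordil are included under nitrates. Nothing says whether they count as antihypertensives.

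**3. Consequence for each definition if the pull follows Table 2.**

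- New diagnosis: a patient with no prior code whose only drug in the preceding year is unlisted appears untreated. Once coded, that patient enters the new-diagnosis group instead of being screened out.
- Initiation: a first prescription for an unlisted drug is not seen. The event is missing, or is replaced by a later listed drug.
- Intensification: adding an unlisted drug, raising its dose or switching to it is not seen.

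So time-to-initiate and time-to-intensify lose endpoints, and the split between new and established diagnoses, which also defines the two time-to-control measures, is misclassified.

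**4. Size.** The documents do not say how often unlisted drugs are used. Let m be the share of true initiation or intensification events that involve only an unlisted drug (assumed). Missed events per 1,000 = 1,000 × m:

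- m = 2%: 20
- m = 5%: 50
- m = 10%: 100
- m = 20%: 200

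**5. Would anything else in the plan catch it?** The refinement of the measures described for Aim 2 in Section 7.1 covers exclusions of readings, visit types and populations; it does not name the drug list. Section 5.3 cites Table 3 as well, and Table 3 records all current medications. But that table is headed as for Aim 3B only, its rows are the enrolment visit and weekly calls, and Section 5.4 gives only Tables 1 and 2 for Aims 1, 2 and 3A. It does not fill the gap.

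**The case against.** The strongest reply is that no sentence limits the pull to Table 2, and that Section 4.0 promises a guideline-based list. The team may intend that list to drive the query, with Table 2 as a working sketch. This stands in part: a restricted pull is an inference, not a stated rule. But Table 2 is the only list that anyone running the query would find in the protocol, and nothing says that the Section 4.0 list overrides it. The mismatch needs correcting on either reading.

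Several stronger readings are tempting and are not supported:

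- *Starting a nitrate for angina will count as intensification.* No passage says so. Nitrates have their own column and can be dropped at analysis. The defect is only that their role is unstated.
- *The error cannot be repaired.* This is true within one extract. The source is a retrospective EMR, so a second query is possible in principle. Section 5.5 keeps identifying information for at most 2 years from study initiation, which limits the time for re-linking.
- *The error works against nephrology and cardiology clinics.* The documents do not show where unlisted drugs are prescribed. The planned contrast also pools those clinics with primary care and internal medicine.
- *Time-to-intensify is lengthened by a calculable number of days.* One could take a true mean of 60 days, 5% to 15% missed events and a wait of 90 to 180 days to the next counted change, giving 60 + 0.05 × 90 = 64.5 to 60 + 0.15 × 180 = 87 days. All of these inputs are assumed. Section 4.0 also starts the clock at the last above-goal reading. For one patient with a 90-day wait, the recorded interval is 60 + 90 = 150 days if no further above-goal reading occurs, but 0 days if one is taken on the day of the next counted change. Even the sign of the shift is not fixed.

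**Conclusion.** The point holds as an unreconciled mismatch between Section 5.4 and Section 4.0 with a definite consequence: if the pull follows Table 2 as written, some real initiations and intensifications are recorded as no action, and some treated patients are counted as new diagnoses. It should be corrected before extraction.

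The omissions are certain from the table, given ordinary pharmacological classification. The misclassification depends on the query following Table 2. Its frequency is unknown; the 20 to 200 missed events per 1,000 rest on an assumed share of 2% to 20%. Neither its effect in days nor its direction across clinic types can be derived from the documents.

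The reach is limited to Aims 2 and 3A, although the Aim 3B comparison population could inherit the split between new and established diagnoses. Aim 1 prevalence and control rest on blood pressure and diagnosis codes. Aim 3B's own medication data come from the chart. The Aim 4B trial, the only part the SAP covers, measures adherence with MEMS caps and is unaffected.

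**What to change.** Before extraction:

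- Define the medication pull by the EMR's antihypertensive pharmacologic classes, including fixed-dose combination products, and say that this is the list promised in Section 4.0.
- Revise Table 2 to match it, and have Sections 4.0, 5.3 and 5.4 refer to that one list.
- State that nitrates, if extracted, do not count as antihypertensives in the prior-use, initiation and intensification definitions.

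If the extract has already been taken from Table 2, run a supplementary query for the missing classes while the linking key still exists, and report how many events and new-diagnosis assignments change.

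The cost is a broader query, a revised table and a larger extract to clean. The change concerns how drugs are classified in the data, not how patients are treated.

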5.5 DATA COLLECTION AND STORAGE

- The data for Aims 1, 2 and 3A will be abstracted from the EMR with the assistance of RISCC and stored in a CSMC supported Box file, accessible only to the study investigators

- Data for Aim 3B will be abstracted from the medical chart of each patient. Data will be recorded in an Excel file and stored in a CSMC supported Box file, accessible only to the study investigators
- Data for Aim 4A will be obtained via digital audio recording from interview discussions and will be stored in a CSMS supported Box file, accessible only to the study investigators
- Data for Aim 4B will be obtained via survey instruments and MEMS-cap devices. Data will be recorded in an Excel file and stored in a CSMS supported Box file, accessible only to the study investigators
- Identifying information will be kept for no longer than 2 years from study initiation.
- Identifiers will be stored in a separate file. A non-identifying code will be tagged to each patient and will serve as a 'key' to link identifying data. This key will only be available to the study investigators.
- Prompts and video diaries will be sent and documented using Medallia LivingLens, a secure platform designed to document remote video recordings for qualitative research. Participants will download the Medallia LivingLens application to their smart phone, which will be used to record their video diaries. Videos are then securely sent for review by the research team. All content is captured and stored in a secure Amazon S3 environment. All data at rest is AES-256 encrypted and encrypted in transit with HTTPS. All files in S3 are encrypted as well as all records/documents stored in databases and search indices. All communication to and from the data center is protected via SSL. API Authorization is protected by OAuth. SAML and OAuth are used for SSO integration. Data is backed up and fully redundant to ensure availability of our systems both real time and in the event of failure. Videos are stored with AWS. AWS has been audited and certified against the most stringent attestation standards and enables compliance with regulatory privacy requirements such as GDPR. AWS has been audited on the following standards: SOC 1/SSAE, 16/ISAE 3402 (formerly SAS 70), SOC 2, SOC 3, FISMA, DIACAP, and FedRAMP, PCI DSS Level 1, ISO 9001 / ISO 27001, ITAR, FIPS 140-2, MTCS Level 3.

5.6 CONFIDENTIALITY AND SECURITY OF DATA

- All data will be stored in a CSMC supported Box file.

7.0 STATISTICAL CONSIDERATIONS

7.1 STUDY OUTCOME MEASURES

Analyses will test the following pre-specified hypotheses for each goal:

Aim	Hypotheses
1: Determine cross-sectional prevalence of undiagnosed and uncontrolled hypertension at CSMC, as well as the patient, physician, and clinic characteristics associated with these outcomes.	
 1) Cross-sectional rates of undiagnosed and uncontrolled hypertension at CSMC, based on the 2017 AA/AHA Guidelines, will be similar to national rates (20% and 50%, respectively). 2) Cross-sectional rates of undiagnosed and uncontrolled hypertension will be higher under the 2017 ACC/AHA Guidelines than the JNC-7 Guidelines. 3) Rates of undiagnosed and uncontrolled hypertension will be lower among patients with visits in Primary Care, Internal Medicine, Nephrology, or Cardiology clinics than for patients who only receive care in other clinics.
2: Develop and pilot test new time-to-care and time-to-control measures.	
 1) Data already collected in the EMR can be used to calculate these five new measures of hypertension care.
3A: Assess the validity, responsiveness, and potential utility of the new time-to-care and time-to-control measures.	
 1) Performance on the time-to-care and time-to-control measures will be associated with cross-sectional control rates at the clinic and physician level. 2) Following release of the 2017 ACC/AHA Hypertension Guidelines, performance on the time-to-control measures and cross-sectional control rates will worsen while performance on time-to-care measures will remain stable. 3) Performance on the time-to-care and time-to-control measures will be better for patients with visits in Primary Care, Internal Medicine, Nephrology, and Cardiology clinics than for patients who only receive care in other clinics.
Aim 3B: Pilot study of the new time-to-control measure's responsiveness to more intensive blood pressure monitoring and intervention	
 1) Use of home blood pressure monitors linked the EMR will allow for weekly intervention by a clinical pharmacist, with titration of antihypertensive therapy, according the to 2017 ACC/AHA Hypertension Guidelines 2) The time-to-control period with will be shorter for those enrolled in the pilot study than those in the general population, not provided with home monitoring and weekly clinical pharmacist intervention
Aim 4A: Interview discussions to explore feasibility and acceptability intervention to increase blood pressure medication adherence	
 1) This is an exploratory aim, designed to inform Aim 4B. No a prior hypothesis.
Aim 4B: pilot study to measure the feasibility, acceptability, and efficacy of interventions designed to increase blood pressure medication adherence	
 1) Medication adherence and hypertension control will be greater among treatment groups compared to control group 2) Patients in the incentive group will demonstrate greater routinization compared to both the control group and the message group

For Aim 1, we will use these data to conduct descriptive analyses of rates of blood pressure control among patients with ambulatory care visits at Cedars-Sinai. Next, we will conduct multivariate regression models using blood pressure control as the outcome variable and various patient, physician and clinic characteristics as the independent variables. We will examine how results differ between the 2017 and JNC-7 guidelines.

For Aim 2, we will apply the new time-to-care measures and time-to-control measures to the same dataset. This will involve an iterative process of refinements as we discover issues that warrant the exclusion of certain blood pressure measurements, types of visits, or patient populations. The result will

be both refined measures and descriptive data on the time-to-care and time-to-control for both undiagnosed and uncontrolled hypertension.

For Aim 3A, we will conduct unadjusted and then adjusted multivariate regression analyses assessing whether time-to-care and time-to-control measures are predictors of (i.e., associated with) blood pressure control rates at the physician level. We will perform these analyses at the physician and clinic levels because time-to-control rates are tautologically associated with the presence of control, and because many types of future quality improvement interventions would likely target individual physicians and clinics. We will compare performance on these measures and control rates between patients with visits in Primary Care, Internal Medicine, Nephrology, and Cardiology clinics than for patients who only receive care in other specialty and subspecialty clinics.

Next, we will perform interrupted time-series analyses of changes in the three hypertension measures after 2017 using multivariate regression models. These analyses will examine each hypertension measure (time-to-care, time-to-control, and control rates) as the dependent variable, using the quarter year as the independent variable. We will examine whether there is a change in intercept or slope during any quarter following the announcement of the ACC/AHA guidelines in 2017. We will then qualitatively compare such changes across the three outcome measures, to assess whether time-to-care is more responsive, as expected.

For Aim 3B, we will conduct unadjusted and then adjusted multivariate regression analyses assessing whether time-to-control measure was different between those enrolled in the pilot study and patients in the non-intervention group.

For Aim 4A, two independent coders will develop a codebook that details the inclusion and exclusion criteria, as well as typical exemplars for each topic or theme. Together, the coders will work to establish inter-coder reliability (evidenced by Cronbach's alpha $\geq .70$) with the goal to converge on a single, agreed upon meaning for each thematic area. For each topic, they will identify the range of themes mentioned, which were most and least salient, and which were discussed most and least frequently. This will produce research reports on specific topics describing the range, central tendency, and distribution of each theme, presenting segments of text as exemplars, which will be used to guide the refinement and implementation of the intervention in Aim 4B.

Finally, for Aim 4B, we will conduct unadjusted and then adjusted multivariate regression analyses assessing whether medication adherence, hypertension control, and adherence to pill-taking routine differ between treatment groups.

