1.0 BACKGROUND, RATIONALE

Routine ambulatory care visits with diverse clinical specialists represent critical missed opportunities to identify and treat patients with undiagnosed or under-treated hypertension. Hypertension is one of the most important cardiovascular risk factors in both its prevalence and the severity of its consequences.¹ Decades of laboratory and clinical studies have demonstrated a clear link between hypertension and devastating cardiovascular events including stroke, myocardial infarction and renal failure.²⁻⁸ Despite the clear risk, half of hypertensive individuals have blood pressures that exceed current standards for control (<130/80), including nearly 20% of hypertensive individuals who have not yet been given a diagnosis.^{1,9} The high rates of undiagnosed and uncontrolled hypertension appear largely due to lack of recognition or insufficient action by clinicians and health systems, rather than lack of access to care: 82% of individuals with uncontrolled hypertension have a routine place of care and nearly two thirds had at least two ambulatory care visits in the past year.¹⁰ Blood pressure is routinely documented during most ambulatory visits, even in specialty clinics like ophthalmology and orthopedics. Moreover, electronic medical record systems (EMRs) have been widely adopted in outpatient clinics,¹¹ and EMR data that is routinely recorded during clinical encounters can accurately identify patients with undiagnosed or uncontrolled hypertension.¹²⁻¹⁶ This means that health systems already have the data and technical expertise needed to identify patients with undiagnosed and undertreated hypertension. However, few health systems leverage these resources, probably because the feasibility and benefits of doing so have not been demonstrated.

As such, our proposed research program will leverage the capabilities of the EMR to in the detection and treatment of uncontrolled hypertension. Via a future NHLBI-funded K23 Career Development Award, we will achieve two long-term goals. First, we will demonstrate how health systems can use the EMR for the surveillance and detection of undiagnosed and under-treated hypertension. Second, we will develop and test health system-based interventions aimed at reducing the time that hypertensive patients spend without a diagnosis, intensified treatment, or optimal control. We plan to use

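### Aim 1 compares a diagnosis-coded rate of uncontrolled hypertension with a national 50% that also counts undiagnosed patients

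*Protocol*

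**What the plan says.** Three places in the protocol bear on this.

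- **Section 7.1, Aim 1 hypothesis 1.** The hypothesis concerns "Cross-sectional rates of undiagnosed and uncontrolled hypertension at CSMC" under the 2017 guideline and says that they "will be similar to national rates (20% and 50%, respectively"). The last word of that quote ties 20% to undiagnosed and 50% to uncontrolled. No denominator is given, and no margin defines similarity.
- **Section 1.0, the source of both figures.** It says that "half of hypertensive individuals have blood pressures that exceed current standards for control (<130/80"), and continues "including nearly 20% of hypertensive individuals who have not yet been given a diagnosis". The undiagnosed are part of the half.
- **Section 4.0, the study definitions.** Undiagnosed hypertension is two outpatient readings at or above 130/80 "without an ICD-9/10 code for hypertension in the preceding year". For the other category, "uncontrolled hypertension will be defined using the same blood pressure criterion but patients will have an ICD-9/10 code for hypertension". One group lacks a code and the other has one, so no patient can be in both at the same time.

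The Aim 1 analysis text in section 7.1 adds that there will be "descriptive analyses of rates of blood pressure control among patients with ambulatory care visits at Cedars-Sinai". The SAP covers only the adherence trial and does not mention this benchmark.

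**The concern.** The 50% describes a total, and the study's uncontrolled category is one part of that total. Comparing the part with the total favours the site. A health system with exactly the national pattern would report a figure well below 50% and appear to be doing better than the country. Conversely, a site with 50% of its diagnosed patients above goal would be called similar, although on the protocol's own background figures it would be worse.

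This matters because section 2.0 gives Aim 1 the task of documenting how large the problem is at this institution. The reasoning for Aim 3A in the same section starts from whether the prevalence of undiagnosed and uncontrolled hypertension is high. The result is also meant as pilot data for a career-award application. A flattering benchmark would weaken that reading.

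**Working it through.** **Inputs**
- U = 0.50, hypertensives above goal as a share of all hypertensives (Protocol 1.0).
- u = 0.20, undiagnosed hypertensives as a share of all hypertensives, taken literally from Protocol 1.0.
- Undiagnosed and uncontrolled are exclusive categories, separated by the diagnosis code (Protocol 4.0).

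**Step 1: reproduce the plan's figures.** The 20% and 50% in section 7.1 are the two figures in section 1.0, carried over correctly. There is no slip in the numbers themselves. The question is what each one counts.

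**Step 2: the part of the 50% that carries a diagnosis.**
- Share of all hypertensives: U − u = 0.50 − 0.20 = 0.30.
- Share of diagnosed hypertensives: (U − u)/(1 − u) = 0.30/0.80 = 0.375.

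**Step 3: the other parse of the sentence.** If the 20% is a share of the above-goal half, then u = 0.20 × 0.50 = 0.10.
- Share of all hypertensives: 0.50 − 0.10 = 0.40.
- Share of diagnosed hypertensives: 0.40/0.90 = 0.444.

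**Step 4: distance from the 50% benchmark.**

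| Reading of the 20% | Denominator | Implied national rate | 50% minus implied rate |
|---|---|---|---|
| Of all hypertensives (literal) | All hypertensives | 30% | 20 points |
| Of all hypertensives (literal) | Diagnosed hypertensives | 37.5% | 12.5 points |
| Of the above-goal half | All hypertensives | 40% | 10 points |
| Of the above-goal half | Diagnosed hypertensives | 44.4% | 5.6 points |

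The background says nearly 20%. Taking that as 17% to 20% (my assumption), the literal reading gives 30% to 33% of all hypertensives (0.50 − 0.17 = 0.33) and 37.5% to 39.8% of the diagnosed (0.33/0.83 = 0.398).

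**Step 5: reverse check.** Suppose that 50% did belong to the coded category, with u = 0.20.
- If both rates are shares of all hypertensives, the total above goal is 0.20 + 0.50 = 0.70.
- If the 50% is a share of the diagnosed only, the total is 0.20 + 0.80 × 0.50 = 0.60.

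Neither agrees with the half stated in section 1.0.

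**Step 6: could sampling error hide the gap?** The protocol does not give the number of hypertensives. Section 7.2 expects about 75,000 records in all. With an assumed 10,000 hypertensives and a rate of 0.375, the 95% half-width is 1.96 × √(0.375 × 0.625/10,000) = 0.0095, or about 1 point. Even the smallest gap in the table is several times that.

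**The case against.** The strongest reply is that Aim 1 may use uncontrolled to mean simply above goal. Section 4.0 first defines blood pressure control as below 130/80 with no mention of a code. The Aim 1 analysis text likewise speaks of control rates among outpatients. The code-based split comes in the paragraph that builds the time-to-care and time-to-control measures. If Aim 1 means everyone with hypertension above goal, 50% is the right comparator. It would therefore go too far to infer that 50% is wrong on every reading. What does not stand is that this reply removes the problem. Hypothesis 1 names undiagnosed and uncontrolled side by side, and the only definition given for uncontrolled hypertension requires a code.

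Three further limits stand.

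- A reader might want to put 30% or 37.5% in place of 50%. The documents do not support that. The study's undiagnosed group depends on coding in the preceding year and on two raised readings, whereas section 1.0 refers to people never given a diagnosis. Hypothesis 1 also names no denominator. If it is all outpatients, none of these shares applies directly.
- A reader might infer that an excess of more than 10 points would pass as similar. That holds only on the literal parse; on the other the gap is 10 or 5.6 points.
- A reader might note that the references cited for these rates date from 2013 and 2016 and infer that they used a different threshold. The documents do not show this, and section 1.0 attaches the 130/80 goal to the figure. It can be no more than a query to the sponsor.

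The consequences are also limited. Hypothesis 1 has no margin and no formal test, and the sample-size text does not use either figure.

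**Conclusion.** The mismatch is real but minor. Followed as written, the plan sets a coded-only rate against a rate that includes the uncoded. The apparent advantage to a site at the national level is 12.5 to 20 points on the literal reading of the background and 5.6 to 10 points on the alternative.

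These sizes rest on two assumptions: that the section 1.0 figures are taken at face value, and that the denominator is either all or diagnosed hypertensives. They illustrate the direction and rough size of the problem and are not replacement benchmarks. The estimated prevalences at the site would be the same whichever national figure is cited. The Aim 4B randomised comparison is untouched.

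**What to change.** Reword Aim 1 hypothesis 1 as follows.

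1. Define the denominator for both rates as all hypertensives: patients with a hypertension code, plus those without one who meet the blood pressure criterion.
2. Compare 50% with the study's undiagnosed and uncontrolled patients combined, over that denominator.
3. Keep 20% as the comparator for undiagnosed patients, over the same denominator.
4. If a coded-only rate is also to be benchmarked, name its denominator and take a national rate with a matching definition from the source. The 30% and 37.5% above should serve as illustration only.

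The cost is a change of protocol wording. It needs no new data, and the combined rate can be formed from variables already being extracted.
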